### 14.6. Secondary Analyses

#### Phase 2

##### Motion Detection

The motion detection metric will be analyzed for the Spherical wearer subject group only using a linear mixed model. The analysis will be conducted on the ITT population. The model will include lens type, lens sequence, and period as fixed effects. Other baseline and subject characteristics such as age, gender, race, and iris color will be included as fixed covariates when appropriate. An UN covariance matrix will be used to model the residual errors among observations within the same subject at the two study periods (R-side). If the model fails to converge, a CS matrix may be considered. The Kenward and Roger method will be used for the denominator degree of freedom.

##### Hypothesis Testing

The null and alternative hypotheses for testing superiority of the Test relative to the Control with respect to mean motion detection within the Spherical wearer subject group are as follows:

$$H_0: \mu_T - \mu_C \geq 0$$
$$H_A: \mu_T - \mu_C < 0$$

where  $\mu_T$  and  $\mu_C$  represent mean motion detection (i.e., distance needed to detect that movement) for the Test and Control lenses, respectively. The one-sided adjusted confidence interval for the LS mean difference (Test – Control) and associated p-value will be calculated to test statistical superiority. Superiority of the Test lens relative to the Control will be declared if the adjusted upper confidence limit is less than 0.

##### Brightness Perception

The brightness perception (LRE) will be analyzed for the Multifocal wearers subject group only using a linear mixed model. The analysis will be conducted on the ITT population. The model will include lens type, lens sequence, period, and natural scene as fixed effects. Other subject characteristics such as age, gender, race, and iris color will be included as fixed covariates when appropriate. An UN covariance matrix will be used to model the residual errors of within-subject repeated measures (R-side). If the model fails to converge, a CS matrix may be considered. The Kenward and Roger method will be used for the denominator degree of freedom.

The null and alternative hypotheses for testing superiority of the Test relative to the Control with respect to mean brightness perception within the Multifocal wearers subject group are as follows:

$$H_0: \mu_T - \mu_C \leq 0$$
$$H_A: \mu_T - \mu_C > 0$$

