### **Details of the method**

The evaluation will involve simple tests of stimulus brightness based on brightness matching: in essence, the investigators will set the scene at a moderate brightness and the subject will adjust the standard (now the dependent outcome) to match. A projector with a high-intensity xenon source will be used to project natural scenes for binocular viewing. A total of five scenes will be selected that vary in their short- mid- and long-wave composition. Participants will adjust a neutral density wedge that controls the intensity of a light stimulus presented next to the natural scene. The log-relative energy at which the standard and scene match to the observer will be recorded.

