# **Clinical Study Protocol**

## **Johnson & Johnson Vision**

Primary Endpoints for Sphere and Multifocal wearers:

1. Visual Range (tested binocularly at 8 cycles per degree). Visual range is defined as the log relative energy of simulated haze needed to obscure an otherwise high contrast grating target. Better visual range is indicated by a higher log-relative energy (LRE) of simulated haze (more haze) to obscure an otherwise highly visible target.

Secondary Endpoints:

1. For Spherical wearers - Motion Detection (tested binocularly). Motion detection is defined as the distance needed (in mm) to determine that a test light has moved from a standard position. Better motion detection is indicated by a smaller distance needed to detect that movement has occurred.
2. For Multifocal wearers - Brightness Perception Score (tested binocularly). Brightness perception is defined as the log- relative energy needed to match a standard stimulus to a natural scene, across 10 different projected scenes. The perception of brighter image is indicated by a higher log-relative energy (LRE) needed to match the initially dim standard to the target. The top 5 scenes will be averaged for each subject.

Exploratory Endpoints:

1. For Spherical wearers – brightness perception
2. For Multifocal wearers – motion detection
3. For Toric wearers – visual range, motion detection, and brightness perception
4. Biomicroscopy (all contact lens wearers)

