### **14.2. Sample Size Justification**

Sample size for Phase 1 was not determined on the basis of statistical considerations because it is primarily for the collecting clinical data to calculate the required sample size for Phase 2.

Sample size requirements for Phase 2 were based on assumptions derived from the analysis of selected data collected in Phase 1. It was calculated that the total sample size of 120 subjects to complete (40 per group) the study provides at least 90% power to test each primary and secondary hypothesis. The sample size and power calculations were performed using a paired sample *t*-test approach (exact method) in PASS (NCSS, 2021).

A gate-keeping approach will be used to control the study-wise Type I error rate at the one-sided 0.025 level and adjust for multiplicity due to multiple efficacy endpoints of interest in combination of Bonferroni adjustment. The null hypothesis for the primary efficacy endpoints has to be rejected at one-sided alpha level of 0.025 first, in order to propagate the full alpha to the secondary family of hypothesis tests. The Bonferroni approach will apply then to testing the secondary efficacy endpoints.

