# Clinical Study Protocol

## Johnson & Johnson Vision

### 14.4. Level of Statistical Significance

Although the Test and Control lenses are senofilcon A based lenses with and without the new UV/HEV filter, respectively, the study lenses assigned to each subject group will be different with different optical designs specifically for vision correction of the sphere, multifocal, and toric (astigmatism) lens wearers. Therefore, the planned hypotheses in Phase 2 will be tested separately for each subject group without Type I error adjustment across the three subject groups, due to different optical designs of the study lenses for different groups. The primary hypothesis for each subject group will be tested using a one-sided Type I error rate of 0.025. The secondary hypotheses will be tested only when the primary hypothesis is met for the same subject group. For secondary hypotheses, the Type I error rate will be adjusted using the Bonferroni approach for the two secondary hypotheses and each secondary hypothesis will be tested using the Bonferroni adjusted one-sided Type I error rate 0.0125 (i.e., one-sided 0.025/2).

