### **14.7. Other Exploratory Analysis**

For Toric wearers, visual range, and brightness perception will be analyzed and tested in the same manner as described for primary and secondary endpoints.

All other exploratory endpoints will be descriptively summarized

Other exploratory analysis may be conducted at the discretion of the study responsible clinician.

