## **15. DATA HANDLING AND RECORD KEEPING/ARCHIVING**

# Clinical Study Protocol

## Johnson & Johnson Vision

### 15.1. Electronic Case Report Form/Data Collection

The data for this study will be captured first on a paper case report form (CRF) to be stored on the study site, so that the investigator conducting the psychophysical testing may perform necessary calculations. After calculations are performed, the data will be captured on electronic case report forms (eCRFs) using the Clario EDC system. An authorized data originator will enter study data into the eCRFs using the EDC system. Data collected on equipment that is not captured in EDC will be formatted to the specification of the JJVC database manager and sent to JJVC for analysis.

External data sources for this study include: Not Applicable

The clinical data will be recorded on dedicated eCRFs specifically designed to match the study procedures for each visit. Only specifically delegated staff can enter data on a CRF. Once completed, the eCRFs will be reviewed for accuracy and completeness and signed by the Investigator. The sponsor or sponsor's representatives will be authorized to gain access to the subject recordation for the purposes of monitoring and auditing the study.

Edit checks, electronic queries, and audit trails are built into the system to ensure accurate and complete data collection. Data will be transmitted from the clinical site to a secure central database as forms are completed or updated, ensuring information accuracy, security, and confidentiality. After the final database lock, the Investigator will be provided with Individual Patient Profiles (IPP) including the full audit trail on electronic media in PDF format for all of the study data. The IPP must be retained in the study files as a certified copy of the source data for the study.

The content and structure of the eCRFs are compliant with ISO14155:2020.

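### The multifocal brightness endpoint is one averaged score per subject, but its Section 14.6 model needs scene-level data, and fitting that model literally does not hold the 0.0125 level

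*Combined protocol and SAP*

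**What the plan says.** - **Endpoint (Section 2.2).** Brightness is matched across ten projected scenes, and "The top 5 scenes will be averaged for each subject". Neither the ranking variable nor whether ranking is done per lens is given.
- **Method (Section 1, part B).** "A total of five scenes will be selected that vary in their short- mid- and long-wave composition".
- **Model (Section 14.6, Brightness Perception).** "The model will include lens type, lens sequence, period, and natural scene as fixed effects". The residual matrix is unstructured (UN) over the within-subject repeated measures, with Kenward-Roger degrees of freedom. The fallback is compound symmetry (CS): "If the model fails to converge, a CS matrix may be considered".
- **Sizing (Section 14.2).** "The sample size and power calculations were performed using a paired sample" t-test, which uses one difference per subject. Table 9 gives SD 0.20, effect size 0.70, power 0.91 and n = 29 for this endpoint.
- **Level (Section 14.4).** "each secondary hypothesis will be tested using the Bonferroni adjusted one-sided Type I error rate 0.0125".
- **Data flow (Section 15.1).** The site first calculates on paper. "After calculations are performed, the data will be captured on electronic case report forms (eCRFs) using the Clario EDC system".
- **Reach (Section 14.7).** "For Toric wearers, visual range, and brightness perception will be analyzed and tested in the same manner as described for primary and secondary endpoints".

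**The concern.** A per-subject average has no scene dimension, so Sections 2.2 and 14.6 cannot both be followed. One of them has to give way, and the plan does not say which. The scene count (five or ten), the meaning of the top five, and whether scene values or only an average reach the database are open as well.

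This is the alpha-controlled secondary test for multifocal wearers, and the toric exploratory analysis inherits it. If the layout is settled after data are in hand, the error rate depends on that choice. Under a scene-level layout the planned covariance matrix is very large for about 40 subjects. The fallback matrix has no visit-level term, although the lens changes only between visits.

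**Working it through.** **1. The plan's own figure.** Inputs from Table 9 and Section 14.4: effect size 0.70, one-sided alpha 0.0125. Paired t-test power is P(T > t(0.9875; n−1)), with T noncentral t on n−1 df and noncentrality 0.70√n.
- n = 29: 0.912 (stated 0.91).
- n = 40: 0.979.

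Table 9 is reproduced, but for one score per subject and lens, not for a scene-level model.

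**2. Size of the planned UN matrix.** S scenes at two visits give 2S rows per subject and 2S(2S+1)/2 parameters.
- S = 5: 10 × 11/2 = 55.
- S = 10: 20 × 21/2 = 210.

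**3. Type I error of the literal UN fit.** Null data were simulated with subject, subject-by-visit, subject-by-scene and residual variation, 20 subjects per sequence, and fixed lens, sequence, period and scene. The fit was REML with UN and Kenward-Roger.
- Five scenes: 579/32,000 = 0.018.
- Ten scenes: 1,114/21,101 = 0.053.

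A separate simulation, with the SD of the averaged difference set to 0.20 and other assumed variances, gave 0.018 to 0.023 and 0.038 to 0.062. UN converged every time, so the CS fallback might never be reached. Code checks returned the nominal level: 0.0115 and 0.0127 with one scene, and 0.0127 with five scenes and 400 subjects.

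The cause is an understated variance. The averaged score has variance 0.20²/40 = 0.0010.
- Five scenes: true variance of the UN estimate 0.00124 to 0.00131, Kenward-Roger about 0.00113; ratio 1.10 to 1.16.
- Ten scenes: true 0.00182 to 0.00196, Kenward-Roger about 0.00105; ratio 1.73 to 1.87.

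With ten scenes the UN estimate in effect adjusts for 9 scene contrasts at each of 2 visits, leaving 40 − 2 − 18 = 20 df. Kenward-Roger assigns 38. An exact covariate-adjusted test on 20 df gives 0.009 to 0.013.

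**4. The CS fallback.** With one fixed scene set and complete data, CS gives the same point estimate as the average; only its standard error is wrong. It pools the visit, scene and residual mean squares (df 38, 39(S−1), 40(S−1)). Worked case: S = 5, no subject-by-scene variance, and visit variation supplying half the variance of the averaged score. In residual units the visit mean square is 2 and the pooled error is (38×2 + 156 + 160)/354 = 1.107, so the true variance is 2/1.107 = 1.81 times the one used. Results for five to ten scenes:

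| Visit share | No subject-by-scene variance | Subject-by-scene equal to residual |
|---|---|---|
| 0% | 0.0125 | 0.001 |
| 25% | 0.024–0.025 | 0.003–0.004 |
| 50% | about 0.05 | 0.013 |
| 75% | 0.10–0.11 | about 0.05 |

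The documents give none of these variance shares.

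**5. The top-five rule, only if ranked on measured LRE within each lens.** The expected mean of the top five of ten standard normals is 0.739, so with equal means over the ten scenes the shift is 0.739 × (Test SD − Control SD). The standard error is 0.20/√40 = 0.0316. Scene SDs are assumed, with Control at 0.20.

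| Test SD | Shift (LRE) | Rejection rate |
|---|---|---|
| 0.25 | +0.037 | 0.13 |
| 0.22 | +0.015 | 0.037 |
| 0.20 | 0 | 0.0125 |
| 0.18 | −0.015 | 0.0035 |
| 0.15 | −0.037 | 0.0004 |

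A set fixed in advance has no such shift.

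**6. One averaged score per visit.** The level is 0.0125 by theory; simulated values scattered around it (0.0085 to 0.018).

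**The case against.** The strongest reply is that the scene term is a leftover. Section 14.6 describes the visual-range covariance in nearly the same words, and the motion model refers explicitly to the two periods. Steps 1.45 and 2.34 list brightness as a single item in the same form as visual range. On that reading UN is a 2×2 matrix on the averaged score and the level holds. This is plausible, but it works only by dropping a term that the plan states, which is the proposed correction.

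Other points stand in part:
- Ten scenes could be projected and five scored. If only five are analysed, the relevant UN figure is 0.018, a modest excess. The method section does not mention ten, however, and the scene term would still conflict with the average.
- The top-five rates are false-positive rates only for a null of equal means over all ten scenes. If the within-lens top-five mean is truly the target, the issue is which quantity is estimated. The scene SDs are assumptions.
- The CS figures fall on both sides of 0.0125 and concern a branch that may not be used.
- Section 15.1 also lets equipment data outside the EDC be sent to the sponsor, so scene values may be available. The plan does not say so for brightness.

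**Conclusion.** The point holds. The mismatch between a per-subject average and a scene-level model, together with five scenes in one section and ten in another, follows from the text and is not resolved elsewhere. Confidence in that is high.

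The size is conditional. With 40 complete subjects, normal data and scene rows analysed as Section 14.6 says, UN with Kenward-Roger exceeds 0.0125 modestly with five scenes (about 0.018) and by roughly four times with ten (about 0.053). It exceeded 0.0125 at every variance split tried. The CS and ranking results show that the choice matters but not in which direction.

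This affects one secondary endpoint, tested only after its group's primary, in a feasibility study. It should be fixed, but it does not threaten the primary analysis.

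**What to change.** Before Phase 2 is unmasked:

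1. Reconcile Sections 1 and 2.2 and name one scene set, chosen without reference to Phase 2 outcomes and identical for every subject and both lenses. A pre-fixed five is enough.
2. Average it to one score per subject per visit and analyse that with the visual-range model (lens, sequence, period; UN or CS over the two visits).
3. Delete the scene term from Section 14.6 and state which brightness values are entered in the eCRF.
4. If a scene-level model is kept, replace the UN/CS choice with random subject, subject-by-visit and subject-by-scene effects, and do not drop the subject-by-visit term.
5. Apply the same wording to the toric analysis in Section 14.7.

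The cost is wording only, with no new measurements if scene values are kept on the paper CRF. If the chosen set differs from the one behind Table 9, recompute both the SD (0.20) and the effect size (0.70) from Phase 1, which requires that its scene values were retained. Power may then change. Under the current assumptions 29 subjects still suffice for 0.91, and 40 completers give 0.979.

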# **Clinical Study Protocol**

## **Johnson & Johnson Vision**

where  $\mu_T$  and  $\mu_C$  represent mean brightness perception (i.e., LRE) for the Test and Control lenses, respectively. The one-sided adjusted confidence interval for the LS mean difference (Test – Control) and associated p-value will be calculated to test statistical superiority. Superiority of the Test lens relative to the Control will be declared if the adjusted lower confidence limit is larger than 0.

If a significant sequence effect was observed, only the period 1 data will be analyzed for the corresponding endpoint.

### **14.7. Other Exploratory Analysis**

For Toric wearers, visual range, and brightness perception will be analyzed and tested in the same manner as described for primary and secondary endpoints.

All other exploratory endpoints will be descriptively summarized

Other exploratory analysis may be conducted at the discretion of the study responsible clinician.

### **14.8. Interim Analysis**

This is a two-phase study. Approximately 20 subjects will be targeted to complete Phase 1. An interim analysis will be performed using data collected from Phase 1 to estimate the required sample size for Phase 2 to achieve at least 80% power for testing the primary hypothesis within each subject group. The total sample size for Phase 2 will be approximately 150 subjects maximum, combining statistical with resources and study timing considerations.

The IA will be conducted at completion of Phase 1. The analyses and statistical power calculation for the determination of the Phase 2 sample size will be conducted by the study unmasked biostatistician. No other team members, nor investigators or subjects will know the Phase 1 results or the Phase 1 lens assignment.

Information about how the sample size calculation for Phase 2 will be conducted is located in Section 14.2. Subject accountability and demographics, and the primary and secondary endpoints data collected from Phase 1 will also be descriptive summarized for the interim analysis.

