# **Clinical Study Protocol**

## **Johnson & Johnson Vision**

Sample Size	
Phase 1 will pilot the procedures and will enroll approximately 24 subjects, with a target of at least 20 to complete (~10 spherical wearers and ~10 multifocal wearers). Data from Phase 1 will be used for sample size estimation for Phase 2. Subjects in Phase 1 will not participate in Phase 2.
 
Phase 2 will execute the same procedures as Phase 1 with a different sample size. Phase 2 sample size will be calculated based on data collected from Phase 1. The total sample size for Phase 2 will be approximately 135 subjects (45 per subject group to enroll and 40 to complete) due to resources and study timing.

Study Duration	
There are two study visits in each phase that will last approximately 2.5-3 hours each and will be separated by 1-14 days.
 

• The study enrollment period for Phase 1 will be approximately 2 weeks, making the duration of Phase 1 approximately 4 weeks.

• Up to 2 weeks will be allotted for statistical analyses.

• The study enrollment period for Phase 2 will be approximately 12 weeks, making the duration of Phase 2 approximately 14 weeks.

• The total study duration is expected to last about 20 weeks.

Anticipated Study Population	
All subjects will be healthy adult male and female volunteers of any race and ethnicity that satisfy the inclusion criteria. All subjects must habitually wear one of three soft contact lenses within the power ranges available for this study:
 

1. Spherical

2. Multifocal

3. Toric (astigmatism)

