### **4.3. Enrollment Target and Study Duration**

#### Phase 1

Phase 1 will have an enrollment target of 24 subjects, with a target of at least 20 to complete. Approximately 10 subjects will wear spherical soft contact lenses and approximately 10 subjects will wear multifocal soft contact lenses. The study will be conducted at a single clinical site. A subject will be considered enrolled upon signing the informed consent form.

There will be 2 visits in total per subject separated by 1-14 days. The enrollment period is 2 weeks making the duration of Phase 1 approximately 4 weeks. If subjects discontinue prior to the final evaluation, then additional subjects may be enrolled at the discretion of the study sponsor to maintain sample size requirements.

#### Phase 2

Phase 1 results are used to estimate the number of subjects required for Phase 2. However, the total sample size for Phase 2 will be approximately 135 subjects due to resources and study timing. The study will be conducted at a single clinical site. A subject will be considered enrolled upon signing the informed consent form. Phase 1 subjects will not be Phase 2 subjects.

There will be 2 visits in total per subject separated by 1-14 days. The enrollment period is 12 weeks making the duration of Phase 2 approximately 14 weeks. If subjects discontinue prior to the final evaluation, then additional subjects may be enrolled at the discretion of the study

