# Clinical Study Protocol

## Johnson & Johnson Vision

The sample size estimates for primary endpoints were calculated using 1-sided Type I error rate of 0.025 for each endpoint. The sample size estimates for the two secondary endpoints were adjusted using a Bonferroni adjustment and calculated using a one-sided Type I error rate of 0.0125 (i.e., one-sided 0.025/2).

While no Toric wearers were enrolled in Phase 1, it is anticipated that the multifocal group would require the largest sample due to simultaneous optics of the multifocal lens and the intraocular scattering that naturally occurs with age, which can both compromise and reduce the quality of vision. Hence it is expected that the sample size required to test endpoints for Toric wearers would be no more than the sample size required for Multifocal wearers. As these endpoints did not have data from Phase 1, all hypotheses for the Toric wearers will be exploratory endpoints.

Table 9 displays the statistical power and associated sample sizes estimates derived for the primary and secondary endpoints for Sphere and Multifocal groups, given the assumed treatment effect sizes. Based on the table below, it is planned that Phase 2 will enroll approximately 135 subjects (45 subjects per group) with the target of 120 subjects (40 subjects per group) to complete the study, assuming approximately a 10% drop-out rate.

Table 9: Assumptions for Power and Sample Size Calculations for The Primary and Secondary Endpoints

Endpoint Type	Endpoint (Subject Group)	Standard Deviation of Paired Differences	Effect Size	Alpha	Power	Sample Size Per Group
Primary	Visual Range (Sphere)	0.10	1.83	0.05	0.94	6
	Visual Range (Multifocal)	0.23	0.52	0.05	0.90	41
Secondary	Motion Detection (Sphere)	1.16	0.99	0.03	0.92	16
	Brightness Perception (Multifocal)	0.20	0.70	0.03	0.91	29

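### Section 14.8 keeps pre-Phase-1 sizing text (80% power, about 150 subjects) not aligned with Section 14.2 (90%, about 135), and the 90% in 14.2 is narrowly missed for multifocal visual range

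*Combined protocol and SAP*

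**What the plan says.** Section 14.8 (Interim Analysis) says that Phase 1 data will be used to size Phase 2 "to achieve at least 80% power for testing the primary hypothesis within each subject group". It then limits the size: "The total sample size for Phase 2 will be approximately 150 subjects maximum, combining statistical with resources and study timing considerations". The section is in the future tense and sends the reader to 14.2 for the method.

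Section 14.2 (Sample Size Justification) is in the past tense. It says that 120 completers, 40 per group, "provides at least 90% power to test each primary and secondary hypothesis". Below that it plans that "Phase 2 will enroll approximately 135 subjects (45 subjects per group) with the target of 120 subjects (40 subjects per group") will complete, with about 10% drop-out. On the error rate it says: "The sample size estimates for primary endpoints were calculated using 1-sided Type I error rate of 0.025 for each endpoint". The secondary endpoints were "calculated using a one-sided Type I error rate of 0.0125 (i.e., one-sided 0.025/2").

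Section 4.3 says that "the total sample size for Phase 2 will be approximately 135 subjects due to resources and study timing". The synopsis gives "approximately 135 subjects (45 per subject group to enroll and 40 to complete) due to resources and study timing". Neither of these two places states a power.

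Table 9 in 14.2 lists the sample size needed per group: 6 and 41 for visual range (sphere, multifocal), 16 for motion detection (sphere) and 29 for brightness perception (multifocal).

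**The concern.** The power level, the set of hypotheses it covers and the Phase 2 total all differ between 14.8 and 14.2, and both versions stand in the current protocol. The Hypotheses section and 14.5 send the reader to 14.8 for detail on the Phase 1 calculation, so a reader following those references meets 80% and 150 first and reaches 90% and 135 only through the onward reference to 14.2. The version 5.0 entry in the change history lists 4.3, 14.2, 14.5, 14.6 and 14.7 as updated, but not 14.8. That fits text left over from before Phase 1.

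The second question lies wholly inside 14.2. It promises at least 90% power for every primary and secondary hypothesis at 40 per group, while its own table asks for 41 for multifocal visual range. At stake is whether the protocol states correctly, and only once, what Phase 2 was designed to deliver.

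**Working it through.** **Inputs.** Effect sizes and sample sizes come from Table 9. The one-sided error rates, 0.025 (primary) and 0.0125 (secondary), come from the text of 14.2, as do the exact paired t-test method and the 10% drop-out.

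**Formula.** With n completers, effect size d (mean paired difference over its SD) and one-sided level α,

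power = 1 − F(t(1−α, n−1); n−1, d√n),

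where F is the noncentral t distribution function with n−1 degrees of freedom and noncentrality d√n.

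**Step 1: reproduce Table 9, then move to 40 completers.**

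| Hypothesis | d | α | Table 9 n | Table 9 power | Recomputed | Power at 40 |
|---|---|---|---|---|---|---|
| Visual range, sphere | 1.83 | 0.025 | 6 | 0.94 | 0.943 | >0.999 |
| Visual range, multifocal | 0.52 | 0.025 | 41 | 0.90 | 0.901 | 0.894 |
| Motion detection, sphere | 0.99 | 0.0125 | 16 | 0.92 | 0.916 | >0.999 |
| Brightness, multifocal | 0.70 | 0.0125 | 29 | 0.91 | 0.912 | 0.979 |

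All four rows reproduce at the error rates given in the text. The alpha column of Table 9 shows 0.05 and 0.03, which fit as two-sided equivalents (2 × 0.025 = 0.05; 2 × 0.0125 = 0.025, rounded to 0.03). Read as one-sided 0.05, multifocal visual range would have power 0.948 at 41, not 0.90.

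**Step 2: the limiting hypothesis in detail.** For multifocal visual range:

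- n = 40: noncentrality 0.52 × √40 = 3.289, critical value t(0.975, 39) = 2.023, power 0.894.
- n = 41: noncentrality 0.52 × √41 = 3.330, critical value t(0.975, 40) = 2.021, power 0.901.

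The effect size is printed to two decimals. Over 0.515 to 0.525, power at 40 runs from 0.888 to 0.899, so it stays below 0.90 throughout. With n−2 degrees of freedom, as in a 2×2 crossover with a period effect, it is 0.893.

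**Step 3: enrolment.** 40 / 0.9 = 44.4, rounded up to 45 per group; 45 × 3 = 135. The plan's total reproduces.

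**Step 4: what the 14.8 figures imply.** For multifocal visual range, 80% power needs 32 completers (0.813; 31 gives 0.79997). With 10% drop-out, 32 / 0.9 = 35.6, so 36 per group and 36 × 3 = 108 in total. So 150 is not the size that an 80% target produces. It is only an upper limit, and 135 lies below it, just as 0.894 lies above 0.80.

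**The case against.** The strongest reply is that nothing conflicts. Section 14.8 sets a rule before the calculation (a minimum power and a maximum size), and 14.2 reports the result, which satisfies both. Section 14.8 points to 14.2, and the operative total of about 135 appears in the synopsis, 4.3 and 14.2. This largely stands: there are not two incompatible designs, and a reader who reaches 14.2 can see what was planned. What remains is that 14.8 still presents a completed calculation as pending, with figures that were not carried forward.

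On the power, it can be said that 0.894 is close enough to 0.90, and that a normal approximation gives 0.908 at 40. The first part is fair as to adequacy. The second does not help, because 14.2 says the exact method was used and Table 9's 41 agrees with that method. The words at least are therefore not met.

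A reader might infer more than the documents support:

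- *That the 90% claim holds under one total and fails under the other.* Section 14.2 ties the claim to 40 completers, not to an enrolment figure. The gap between 40 and 41 would remain if 14.8 were deleted. Giving 150 a power of 0.927 needs an equal split and 10% drop-out (150 / 3 × 0.9 = 45 completers), which 14.8 does not state; the same 0.927 follows from 135 if all 45 in the multifocal group complete.
- *That enrolment is open-ended.* Section 4.3 allows added subjects only where subjects discontinue, and only to maintain the required sample size.
- *That lens supply is in doubt.* Section 6.1 gives minimum quantities per SKU, and the change history says they were updated to the revised sample size. Nothing ties them to 150.
- *That 4.3 and the synopsis also promise 90%.* They give the 135 without a power figure.

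**Conclusion.** The point holds as a minor consistency correction in two parts. First, 14.8 carries a superseded power target and upper limit beside the completed calculation in 14.2; the totals differ by 15 subjects (150 − 135), but the design in 14.2 does not breach either figure in 14.8. Second, the 14.2 statement is too high for one hypothesis of four: multifocal visual range has power 0.894 at the planned 40 completers, about 0.6 of a percentage point below 90% (0.1 to 1.2 points over the rounding of the effect size), a shortfall of one completer in that group.

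This rests on the Table 9 effect sizes, the one-sided levels in the text and the paired t-test that the plan used for sizing. Neither part bears on the adequacy of the sample size, on error control or on the analysis.

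**What to change.** Rewrite 14.8 in the past tense: the Phase 1 calculation is complete, the power target is the one in 14.2, and the Phase 2 total is about 135 (45 enrolled and 40 completing per group), as in 4.3 and the synopsis. Remove the 80% and 150 figures, or label them as the limits set before Phase 1.

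In 14.2, replace the blanket 90% statement with the power per hypothesis at 40 completers: above 99.9% for sphere visual range, about 89% for multifocal visual range, above 99.9% for sphere motion detection and about 98% for multifocal brightness perception.

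The cost is protocol wording only. Enrolment, design and analysis stay as they are.
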